17.3. TERTIARY EFFICACY

17.3.1. TERTIARY EFFICACY VARIABLES & DERIVATIONS

The tertiary efficacy endpoints are:

- Absolute change and percent change from baseline to Week 52 in LDL-C
- Percent change from baseline to Weeks 24 and 52 in non-HDL-C, TC, apoB, and hsCRP
- Percent change from baseline to Weeks 12, 24, and 52 in TG and HDL-C

17.3.2. MISSING DATA METHODS FOR TERTIARY EFFICACY VARIABLES

No missing data imputation will be used for the tertiary analyses.

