2.3. TERTIARY OBJECTIVES

The tertiary objectives are:

- To evaluate the long-term treatment (52 weeks) with bempedoic acid 180 mg/day versus placebo on LDL-C, non-HDL-C, TC, HDL-C, TG, hsCRP, and apoB.
- To evaluate the 52-week safety and tolerability of bempedoic acid 180 mg/day compared to placebo.

[figure not shown]
Statistical Analysis Plan

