7. STATISTICAL CONSIDERATIONS

7.1. SAMPLE SIZE

The primary efficacy endpoint for this study is the percent change from baseline to Week 12 in LDL-C.

The sample size of 500 randomized patients in the bempedoic acid 180 mg group and 250 randomized patients in the placebo group is expected to provide more than 95% power to detect a difference of 15% in the percent change from baseline to Week 12 in LDL-C between the bempedoic acid treatment group and the placebo group. This calculation is based on a 2-sided t-test at the 5% level of significance ($\alpha = 0.05$) and a common standard deviation of 15%. The sample size of 500 randomized patients in the bempedoic acid 180 mg group and 250 randomized patients in the placebo group gives a total study sample size of 750.

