17.2.3.4. Observed Data Analysis

The observed case data with no imputation for missing data will be used in sensitivity analyses for primary and key secondary endpoints to explore any difference between a observed analysis vs. missing data imputation using PMM method.

17.2.4. **SUBGROUP ANALYSIS OF PRIMARY EFFICACY VARIABLE**

The primary endpoint for LDL-C will be analysed within subgroups below using the same analysis method previously described. The treatment and subgroup interaction will be examined by including the interaction term in the ANCOVA model for the overall population first. No imputation will be performed on missing data for subgroup analyses. In case the number of subjects within a subgroup is too small, e.g. less than 5% of the overall population, the analyses may not be performed or the subgroup levels may be combined. Forest plots for the primary efficacy variable will also be presented.

- CV risk category (HeFH (with or without ASCVD) vs. ASCVD only)
- Baseline statin intensity (Low or Moderate, vs. High)
- Baseline LDL category ($<130\text{mg/dL}$, $\geq 130\text{ mg/dL}$ and $< 160\text{ mg/dL}$, $\geq 160\text{mg/dL}$) (efficacy only)
- History of diabetes (yes vs.no)
- Age ($< 65\text{ yrs.}$ vs. $\geq 65\text{ yrs.}$ and $<75\text{ yrs}$ vs. $\geq 75\text{ yrs}$)
- Race (White vs. other)
- Gender (male vs. female)
- Region (North America vs. EU)
- BMI category (< 25 vs. $25 - < 30$ vs. $\geq 30\text{ kg/ m}^2$)

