17.3.3. ANALYSIS OF TERTIARY EFFICACY VARIABLES

Tertiary efficacy endpoints of LDL-C, non-HDL-C, TC and ApoB will be analyzed using the same ANCOVA model described in [17.1.2](#). Each statistical comparison will be conducted at significant level of 0.05.

hsCRP will be analysed using non-parametric Wilcoxon rank sum test as described in [17.2.1](#).

In addition, the LDL-C endpoint at week 52 will be analyzed with patients in the FAS who did not receive additional lipid-lowering therapy by that time point (by week 52). Only observed case data will be used (no imputation for missing data).

For endpoint of HDL-C and TG at week 12, 24, and 52 summary statistics will be provided for actual value, change and percent change at each visit by treatment group.

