APPENDIX 4. DETAILS OF MULTIPLE IMPUTATION METHOD

Missing Week 12 values will be imputed based on baseline values. The following table details the possible cohorts and which cohorts will be used for imputation. Missing Week 24 values will be imputed in the same way.

	Treatment	Week 12 Value	On Treatment at Week 12	Imputation Cohort(s)
1	Placebo	Missing	Yes	Cohort 5: Placebo patients with non-missing Week 12
2	BA	Missing	Yes	Cohorts 6 and 8 BA patients with non-missing Week 12
3	placebo	Missing	No	Cohort 5: Placebo patients with non-missing Week 12
4	BA	Missing	No	Cohorts 5 and 7 Placebo patients with non-missing Week 12 and not on treatment
5	placebo	Non-missing	Yes	
6	BA	Non-missing	Yes	
7	placebo	Non-missing	No	
8	BA	Non-missing	No	

Imputation code for Cohorts 1-3.

```
proc mi;
where cohort in(1,2,3,5,6,8);
class trt01pn strata;
monotone regression;
var trt01pn strata base aval;
run;
```

Imputation code for Cohort 4.

```
proc mi;
where cohort in(4,5,7);
class strata;
monotone regression;
var strata base aval;
run;
```

Statistical Analysis Plan

Two hundred imputed datasets will be created, with results from the analysis of each imputed dataset (ANCOVA) combined using Rubin's method.

[REDACTED]

[REDACTED]

[REDACTED]

[REDACTED]

Version Number:
Version Date:

0.5
14June2018

Statistical Analysis Plan

Adverse Event Terms per Protocol	Associated MedDRA Preferred Terms
	increased
Renal disorders	Creatinine renal clearance abnormal
Renal disorders	Creatinine renal clearance decreased
Renal disorders	Glomerular filtration rate abnormal
Renal disorders	Glomerular filtration rate decreased
Renal disorders	Oliguria
Renal disorders	Prerenal failure
Renal disorders	Renal failure
Renal disorders	Renal function test abnormal
Renal disorders	Renal impairment
Gout	Gout

[REDACTED]

[REDACTED]

[REDACTED]

[REDACTED]

Addendum to Statistical Analysis Plan

Title: A LONG-TERM, RANDOMIZED, DOUBLE-BLIND, PLACEBO-CONTROLLED, MULTICENTER STUDY TO EVALUATE THE EFFICACY OF BEMPEDOIC ACID (ETC-1002) IN PATIENTS WITH HYPERLIPIDEMIA AT HIGH CARDIOVASCULAR RISK NOT ADEQUATELY CONTROLLED BY THEIR LIPID-MODIFYING THERAPYE

Protocol: ETC-1002-047

Clinical Phase: 3

Product: ETC-1002

Date: Dec 17, 2018

Addendum to the Statistical Analysis Plan for Study 1002-047

Post-hoc Analyses

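### Week 52 LDL-C is analysed on observed cases only, and no planned Week 52 analysis applies the missing-data rule used for LDL-C at Weeks 12 and 24

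*SAP*

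**What the plan says.** SAP 17.1.3 splits patients with a missing Week 12 lipid value by whether they are still taking study drug. Those off drug are assumed to have lost the benefit and are imputed from placebo patients. Those still on drug are imputed from their own randomized arm. SAP 17.2.1 extends the method to the key secondary endpoints, which include percent change in LDL-C at Week 24; Appendix 4 confirms: "Missing Week 24 values will be imputed in the same way".

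Absolute and percent change in LDL-C at Week 52 are tertiary endpoints (SAP 17.3.1). For these, SAP 17.3.2 says "No missing data imputation will be used for the tertiary analyses". SAP 17.3.3 tests Week 52 LDL-C at the 0.05 level with the primary ANCOVA model. It adds one further Week 52 analysis, limited to patients without additional lipid-lowering therapy, which is again observed-case. The sensitivity analyses in SAP 17.2.3 cover only the primary and key secondary endpoints. The post-hoc tables listed in the SAP addendum include no Week 52 LDL-C analysis.

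The 52-week effect is a stated objective in SAP 2.3: "To evaluate the long-term treatment (52 weeks) with bempedoic acid 180 mg/day versus placebo on LDL-C". Protocol 12.6 agrees with the SAP: imputation is confined to the step-down endpoints, and other secondary and tertiary endpoints use observed data.

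**The concern.** The SAP's premise is that a patient who has stopped drug and has no lipid value should not be credited with benefit. Nothing in the documents explains why that should cease to hold after Week 24. Cumulative withdrawal from the study can only stay level or grow by Week 52, and several design features can leave off-drug patients without a Week 52 value:

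- Patients who stop drug and refuse clinic visits are followed by telephone, without lipids (Protocol 10.3.1 and Appendix 1).
- No lipid sample is scheduled between Weeks 24 and 52.
- The Week 52 analysis window opens at Day 310 (SAP 6.4), so lipids from an earlier withdrawal visit do not count.

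Readers will naturally take Weeks 12, 24 and 52 as one durability curve. The main estimates at the first two points discount missing off-drug patients and the third does not. A loss of average effect caused by patients leaving the drug and the clinic would show at Weeks 12 and 24 but not at Week 52. The stake is interpretation: Week 52 lies outside the step-down sequence (SAP 7.5), so no type I error claim depends on it.

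**Working it through.** **The plan's own figure.** SAP 7.1 claims "more than 95% power to detect a difference of 15" percent, "based on a 2-sided t-test at the 5% level of significance", with "a common standard deviation of 15" percent and 500 versus 250 patients.

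- SE = 15 × √(1/250 + 1/500) = 1.162
- Noncentrality = 15 / 1.162 = 12.91; power is above 99.9%, so the claim reproduces as a lower bound (about 20 placebo and 40 active patients would give 95%)
- Planning 95% CI half-width = 1.96 × 1.162 = 2.28 points

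Power is therefore not at issue. SAP 7.1 gives no dropout or missing-data rate, so f has to be assumed.

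**Formula.** Let E be the observed-case treatment effect at a visit. In the bempedoic acid arm:

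- share f, missing and off drug: placebo-based value, effect 0
- share g, missing and on drug: imputed from observed bempedoic acid patients (cohorts 6 and 8 in Appendix 4), effect E
- the remainder, observed on or off drug: effect E on average

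Missing placebo patients are imputed from placebo and change nothing. The effect under the primary rule is therefore (1 − f) × E, the gap is f × E, and observed-case / primary rule = 1/(1 − f).

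**Numbers.** E = 15 is the planning difference in SAP 7.1. E = 22 is the Phase 2 figure on top of stable statin in Protocol 4.2.4. The range for f is illustrative.

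| f | 1/(1 − f) | E = 15: primary rule (gap) | E = 22: primary rule (gap) |
|---|---|---|---|
| 0% | 1.000 | 15.0 (0) | 22.0 (0) |
| 4% | 1.042 | 14.4 (0.6) | 21.1 (0.9) |
| 8% | 1.087 | 13.8 (1.2) | 20.2 (1.8) |
| 12% | 1.136 | 13.2 (1.8) | 19.4 (2.6) |

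The gap passes the 2.28-point half-width at f = 2.28/15 = 15% for E = 15, and at 2.28/22 = 10% for E = 22.

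**Simulation check.** 300 trials of 500 versus 250, SD 15, true on-drug effect −15, none off drug; h is the share observed off drug.

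| f, g, h | Observed-case | Appendix 4 model |
|---|---|---|
| 0%, 10%, 10% | −13.34 | −13.33 |
| 5%, 2%, 5% | −14.27 | −13.55 |
| 10%, 2%, 5% | −14.11 | −12.69 |
| 20%, 2%, 5% | −14.12 | −11.31 |

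The gap comes only from f and matches the formula (for example 0.90 × 14.11 = 12.70).

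**Added lipid therapy.** LDL-C threshold notification begins at Week 24 (Protocol 11.1.6.4.1), so it can affect Week 52 but not Week 12. With f = 10%, g = 2%, h = 5%, suppose a share of placebo patients only receives therapy that lowers LDL-C by 25 points (assumed):

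| Placebo share with added therapy | Observed-case | Appendix 4 model |
|---|---|---|
| 0% | −14.09 | −12.67 |
| 5% | −12.81 | −11.53 |
| 10% | −11.75 | −10.55 |
| 20% | −9.08 | −8.16 |

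At Week 52 the two rules still differ by roughly the factor 1/(1 − f). Across visits, added therapy can offset or outweigh that gap.

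**The case against.** The strongest defence is that this is a deliberate, pre-specified choice on which protocol and SAP agree, for an endpoint outside the type I error hierarchy. A simpler missing-data rule for tertiary endpoints is common practice. All of that stands: there is no deviation and no inflated error rate. It does not answer why the one long-term LDL-C estimate has no analysis on the same footing as those at Weeks 12 and 24.

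A second defence is that patients who stop drug are asked to keep attending for fasting lipids (Protocol 10.3.1). This also stands. A reader might take the Week 52 result for an analysis of completers, but it includes off-drug values wherever they were obtained, and these already pull the estimate towards loss of benefit. Only patients both missing and off drug create the gap, and good retention could make it negligible.

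A reader might also extend the point to the subgroups, because SAP 17.2.4 says "No imputation will be performed on missing data for subgroup analyses". The documents do not support that:

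- If two subgroups share an observed effect of 18 but have f of 10% and 4%, the plan shows 18 and 18. The difference appears only under imputation: 18 × 0.90 = 16.2 against 18 × 0.96 = 17.3, or 1.1 points.
- The Appendix 4 model has no subgroup-by-treatment term, so using those datasets for subgroups would be a trade-off.
- SAP 17.2.3.4 already plans an observed-case overall result as a like-for-like comparator, and nothing says that the forest plot carries an imputed overall row.

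**Conclusion.** The point holds for Week 52 LDL-C, as a matter of comparability and interpretation. The missing-data rule changes between Week 24 and Week 52, and no planned Week 52 analysis restores it. At Week 52 itself, the observed-case effect exceeds the value under the primary rule by the factor 1/(1 − f): about 0.6 to 2.6 points for observed effects of 15–22 and f of 4–12%, and nil if f = 0. This rests on an assumed f and on the SAP's own premise that missing off-drug patients resemble placebo patients.

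A reader might infer that the Week 52 effect is overstated relative to the Week 12 primary estimate. That cannot be established. The two visits differ in exposure to added lipid therapy as well as in the missing-data rule. If more placebo patients receive such therapy, the observed Week 52 difference shrinks, so the net direction is undetermined.

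The inconsistency is also narrower than a contrast of whole visits. At Week 24 only percent change in LDL-C is imputed; Week 24 non-HDL-C, TC, apoB and hsCRP are tertiary and observed-case.

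**What to change.** - Add the Appendix 4 pattern-mixture analysis for Week 52 percent change in LDL-C, at least as a sensitivity analysis beside the observed-case result. Specify the reference date that defines off drug for patients with no Week 52 visit; the target Day 365 in SAP 6.4 is a natural choice. State how values after added lipid therapy enter the imputation.
- Use that estimate wherever Weeks 12, 24 and 52 are compared for durability, so that all three follow one rule.
- Report f by arm and visit, with the shares missing on drug and observed off drug, so that readers can judge the gap.

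The addendum says that the planned analyses were completed and the data unblinded, so an analysis added now should be labelled post hoc. The cost is a little more analysis work, mostly re-use of existing code, and a slightly less favourable Week 52 figure if f is above zero.

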17.3.3. ANALYSIS OF TERTIARY EFFICACY VARIABLES

Tertiary efficacy endpoints of LDL-C, non-HDL-C, TC and ApoB will be analyzed using the same ANCOVA model described in [17.1.2](#). Each statistical comparison will be conducted at significant level of 0.05.

hsCRP will be analysed using non-parametric Wilcoxon rank sum test as described in [17.2.1](#).

In addition, the LDL-C endpoint at week 52 will be analyzed with patients in the FAS who did not receive additional lipid-lowering therapy by that time point (by week 52). Only observed case data will be used (no imputation for missing data).

For endpoint of HDL-C and TG at week 12, 24, and 52 summary statistics will be provided for actual value, change and percent change at each visit by treatment group.

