6. Test the percent change from baseline to Week 12 in hs-CRP

In this hierarchical testing structure, each hypothesis is tested at a significance level of 0.05, two-sided. Statistical significance at each step is required in order to test the next hypothesis. If the primary endpoint meets the criteria for statistical significance, then the percent change from baseline to Week 24 in LDL-C will be tested; and so forth.

Percent change from baseline to Week 24 in LDL-C; absolute change from baseline to Weeks 12, 24,

and 52 in LDL-C; percent change from baseline to Weeks 12, 24, and 52 in HDL-C, non-HDL-C, TG, TC, apoB, and hs-CRP will each be analyzed using ANCOVA with treatment group, CV risk (ASCVD only; HeFH with or without ASCVD) and baseline statin intensity (high intensity, moderate intensity, low intensity) as factors and the relevant baseline as a covariate. Baseline for HDL-C, non-HDL-C, TG, and TC will be defined as the mean of the lipid values from Week -1 (Visit S3) and predose Day 1/Week 0 (Visit T1). If a repeat lipid measurement is performed at Week -1 (Visit S3), then baseline will be the mean of the lipid values from the second Week -1 assessment and predose Day 1/Week 0 (Visit T1). Baseline for apoB and hs-CRP will be defined as the predose Day 1/Week 0 (Visit T1) value. Each ANCOVA will be performed using the FAS, with patients included in their randomized treatment group regardless of the treatment they actually received. For each lipid parameter and analysis time point, the LSM and SE will be provided for both treatment groups, along with the placebo-corrected LSM, its 95% CI and associated p-value.

For all continuous efficacy endpoints (percent change from baseline in LDL-C, HDL-C, non-HDL-C, TC, TG, apoB, and hs-CRP; change from baseline in LDL-C; to Weeks 12, 24, and 52, as appropriate), the ANCOVA assumption of normality will be assessed. If non-normality of the data is found at any time point for any parameter, either the data will be transformed so that it is normally distributed or a nonparametric test will be used instead of the planned ANCOVA.

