5.1.3. Tertiary Objectives

- To evaluate the effect of long-term treatment (52 weeks) with bempedoic acid 180 mg/day versus placebo on LDL-C, non-HDL-C, TC, HDL-C, TG, hs-CRP, and apoB.
- To evaluate the long-term (52 weeks) safety and tolerability of bempedoic acid 180 mg/day compared to placebo.

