12. STATISTICS

12.1. General Considerations

The statistical analyses described in this section will be performed as further outlined in a separate Statistical Analysis Plan (SAP). The SAP will supersede the protocol in the event of any differences between the 2 documents in the plans for data analysis, and the protocol will be amended if appropriate. The SAP will be included as an appendix in the clinical study report for this protocol.

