12.6. Secondary and Tertiary Efficacy Endpoints

Key secondary efficacy endpoints are also of interest for this study, in terms of controlling the overall Type I error rate. A gatekeeping or stepdown approach will be used to test the primary efficacy endpoint and then specific secondary efficacy endpoints sequentially in order to preserve the study-wise Type I error rate. The sequence for the stepdown procedure in this study is as follows:

1. Test the primary efficacy endpoint: percent change from baseline to Week 12 in LDL-C
2. Test the percent change from baseline to Week 24 in LDL-C
3. Test the percent change from baseline to Week 12 in non-HDL-C
4. Test the percent change from baseline to Week 12 in TC
5. Test the percent change from baseline to Week 12 in apoB
6. Test the percent change from baseline to Week 12 in hs-CRP

In this hierarchical testing structure, each hypothesis is tested at a significance level of 0.05, two-sided. Statistical significance at each step is required in order to test the next hypothesis. If the primary endpoint meets the criteria for statistical significance, then the percent change from baseline to Week 24 in LDL-C will be tested; and so forth.

In general, change or percent change in lipid parameters at a given time point will be analyzed using similar ANCOVA model for the primary endpoint with treatment group, CV risk (ASCVD only; HeFH with or without ASCVD) and baseline statin intensity (high intensity, moderate intensity, low intensity) as factors and the relevant baseline as a covariate.

Baseline for HDL-C, non-HDL-C, TG, and TC will be defined as the mean of the lipid values from Week -1 (Visit S3) and predose Day 1/Week 0 (Visit T1). If a repeat lipid measurement is performed at Week -1 (Visit S3), then baseline will be the mean of the lipid values from the second Week -1 assessment and predose Day 1/Week 0 (Visit T1). Baseline for apoB and hs-CRP will be defined as the predose Day 1/Week 0 (Visit T1) value.

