Each ANCOVA will be performed using the FAS, with patients included in their randomized treatment group regardless of the treatment they actually received. Same imputation method described for the primary endpoint will be used for those secondary endpoints included in the step-down procedure, while only observed data analysis will be used for other secondary and tertiary endpoints. For each lipid parameter and analysis time point, the LSM and SE will be provided for both treatment groups, along with the placebo-corrected LSM, its 95% CI and associated p-value.

The ANCOVA assumption of normality will be assessed. If non-normality of the data is found at any time point for any parameter, either the data will be transformed so that it is normally distributed or a nonparametric test will be considered instead of the planned ANCOVA.

Percent change from baseline to Week 24 and to Week 52 LDL-C will be analyzed similarly with patients in the FAS who did not receive additional lipid-lowering therapy by that time point (by Week 24 for the Week 24 analysis; by Week 52 for the Week 52 analysis) included in the analyses. Only observed case data will be used (no imputation for missing data). Output from each time point will include the LSM and SE for each treatment group, as well as the placebo-correct LSM, 95% CI, and p-value.

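### SAP 17.3.3 replaces the protocol's ANCOVA for HDL-C and TG with by-arm summaries and gives no reason, so the 52-week comparison with placebo has no planned treatment difference or CI for two of its seven parameters

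*SAP*

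**What the plan says.** Percent change in TG and HDL-C is a declared tertiary endpoint at three time points in both documents (Protocol 5.2.3; SAP 17.3.1: "Percent change from baseline to Weeks 12, 24, and 52 in TG and HDL-C"). The 52-week tertiary objective is the effect of bempedoic acid "versus placebo on LDL-C, non-HDL-C, TC, HDL-C, TG, hs-CRP, and apoB" (Protocol 5.1.3), and SAP 2.3 restates it.

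On method, the protocol synopsis is explicit: "percent change from baseline to Weeks 12, 24, and 52 in HDL-C, non-HDL-C, TG, TC, apoB, and hs-CRP will each be analyzed using ANCOVA". Protocol 12.6 is more general. It says that "change or percent change in lipid parameters at a given time point will be analyzed" with an ANCOVA like the primary one, and adds: "For each lipid parameter and analysis time point, the LSM and SE will be provided for both treatment groups, along with the placebo-corrected LSM", with a 95% CI and p-value. Missing data are not imputed at this tier, "while only observed data analysis will be used for other secondary and tertiary endpoints". Both places allow a transformation or a nonparametric test if the data are not normal.

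SAP 17.3.3 applies the 17.1.2 ANCOVA to LDL-C, non-HDL-C, TC and apoB, and the Wilcoxon method to hsCRP. For the other two lipids it says: "For endpoint of HDL-C and TG at week 12, 24, and 52 summary statistics will be provided for actual value, change and percent change", by visit and treatment group. Protocol 12.1 settles precedence: "The SAP will supersede the protocol in the event of any differences".

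**The concern.** The objective is comparative, and the protocol planned a comparative analysis for these lipids. The governing document describes each arm separately and stops there. TG and HDL-C become the only declared lipid parameters with no between-arm analysis at any time point.

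What is at stake is the reporting of these two lipids. A shift in either direction would appear in the study report without a planned treatment difference, a CI, or adjustment for baseline and randomisation strata. For TG, mean percent change is also sensitive to extreme values. Entry excludes TG only at 500 mg/dL or above (Protocol 7.2), and Protocol 11.1.6.4.2 plans for on-study values above 1000 mg/dL.

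**Working it through.** **1. Method by parameter, current text against current text**

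| Parameter (percent change) | Protocol synopsis | SAP 17.3.3 |
|---|---|---|
| LDL-C, non-HDL-C, TC, apoB | ANCOVA, placebo-corrected LSM, CI, p | ANCOVA |
| hsCRP | ANCOVA, or alternative if non-normal | Wilcoxon |
| HDL-C, TG | ANCOVA, or alternative if non-normal | By-arm summary statistics |

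The Week 52 objective names seven parameters. Five have a between-arm analysis and two do not. Across the endpoint list, 2 lipids x 3 visits = 6 comparisons lack one. Two of these (Week 52) serve a stated objective. The other four (Weeks 12 and 24) rest on the endpoint list alone.

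**2. Is the analysis elsewhere in the SAP?** No.
- Section 18.4 gives by-visit laboratory summaries, and section 18 rules out between-group safety comparisons unless otherwise specified.
- The lipid table in Appendix 3 is produced for the DMC only.
- The addendum lists no TG or HDL-C analysis.

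**3. What a reader could still derive.** SAP Appendix 1 sets the table content as n, mean, SD, quartiles, median, minimum and maximum. An unadjusted interval follows from the by-arm figures: difference in means ± 1.96 x sqrt(SD_b²/n_b + SD_p²/n_p). The baseline- and stratum-adjusted difference does not follow from them. Nor does a Hodges-Lehmann estimate, which needs patient-level values.

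**4. Does sample size explain the omission?** First, the plan's own figure (SAP 7.1: 500 v 250, difference 15, SD 15, two-sided 0.05):
- SE = 15 x sqrt(1/500 + 1/250) = 15 x 0.0775 = 1.162 points.
- 15 / 1.162 = 12.9, so power is about 1.00. The stated figure of more than 95% reproduces.

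The documents give no SD for percent change in TG or HDL-C, so the following is illustration over an assumed range of 15 to 50 points:
- All 750 observed: 95% CI half-width = 1.96 x 0.0775 x SD, about 2.3 points at SD 15 and 7.6 points at SD 50.
- Assumed 20% missing in each arm (400 v 200): the SE is sqrt(1/400 + 1/200) = 0.0866 SD, and the half-width is 1.96 x 0.0866 x SD, about 2.5 and 8.5 points.

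The trial could estimate these differences with useful precision, so size is not a reason to leave them out.

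**5. What adjustment adds.** With correlation r between baseline and percent change, the SE falls by the factor sqrt(1 - r²). For assumed r of 0.2 and 0.4 this is 0.980 and 0.917, so the CI narrows by about 2% to 8%.

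**The case against.** The strongest reply is that little is lost. The by-arm tables carry n, mean and SD, so an unadjusted difference and CI can be computed, and adjustment would tighten it only slightly on the assumed correlations. The tables also carry the median and quartiles, and SAP 17.2.1 adds plots of mean ± SE or median (IQR), which partly answers the worry about extreme TG values. Protocol 12.1 lets the SAP depart from the protocol, and current 12.6 no longer names these lipids, so the explicit commitment survives only in the synopsis.

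Most of that stands, and it limits the point. A reader might infer that any effect could be judged only by eye. The table content in Appendix 1 shows otherwise. A reader might also infer that all six comparisons leave a stated objective unanswered. The objective naming these lipids covers 52 weeks only, and the secondary objectives name neither lipid. Nor is this clearly an isolated slip: SAP 17.2.2 also makes absolute LDL-C change at Weeks 12 and 24 descriptive, although that is a secondary endpoint. A deliberate choice to describe some endpoints is possible.

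What remains is that the SAP states no such choice. Precedence decides which text governs but does not supply a reason. LDL-C also has between-arm analyses elsewhere in the SAP, and TG and HDL-C have none. Skewness does not explain the change, because both documents already provide a nonparametric route.

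**Conclusion.** The conflict is real in current text and the consequence is minor. Percent change in HDL-C and TG has no planned adjusted treatment difference or CI at Week 52, where an objective calls for a comparison with placebo, or at Weeks 12 and 24, where both are listed endpoints. The shortfall is two of the seven parameters in that objective.

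A reader might go further and suspect that error control or the main efficacy claim is touched. The documents do not support that: these endpoints lie outside the step-down procedure in SAP 7.5, and the primary and key secondary analyses do not depend on them.

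The text comparison needs no assumption. The precision figures rest on assumed SDs, assumed correlations and assumed completeness. They show only that the estimate was feasible, not that any conclusion is compromised.

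**What to change.** In SAP 17.3.3:
- Add HDL-C to the observed-case ANCOVA of 17.1.2, with baseline HDL-C as the covariate.
- Analyse TG with the Wilcoxon test and Hodges-Lehmann estimate and CI already specified for hsCRP in 17.2.1. This is not baseline-adjusted, but it is robust to extreme values and uses a method already in the plan.
- Report the treatment difference and 95% CI at Weeks 12, 24 and 52, outside the step-down procedure.
- Keep the summary tables.

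The addendum records that unblinding has taken place. Any analysis added after that point should be labelled as such, with a note that the protocol synopsis had planned a between-arm analysis. If the sponsor wants these endpoints to stay descriptive, the SAP should say why, and the objective and synopsis should be aligned with it.

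The cost is one paragraph and six runs with existing methods, with no new data. The downside is six extra nominal comparisons.
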